## [1] Sample size. Comparison for paired means.

Data:

Mean differences to be detected:	6.442
Standard Deviation of the differences:	8.221
Level of confidence:	95.0%
sults.	

Results:

Stat. Power (%)	Number of Pairs
80.0	15

Inclusion criteria:

- Men and women from 20 to 60 years old

- With Waist-Hip Index. Greater than: 0.84 normal for women. 94 normal for men.

- Body Mass Index that is defined as: Overweight: Between 25-29.9. Obesity: 30 or higher.

- Measurement of Visceral Fat per Inbody greater than 9, which is what is considered Normal.

- Signed informed consent (Annex 1).

Exclusion Criteria:

- Contraindication to the use of radiofrequency: pregnancy, metal prostheses, active infection.

- Patients with a history of cancer, chemotherapy and radiotherapy treatments.

- Not having diabetes or metabolic disease.

MEASUREMENTS

Body Mass Index, Waist-t-Hip ratio and visceral fat:

Body Mass Index is calculated as follows: Body Weight (Kg) ÷ (Height in cm)2

Waist-to-Hip Ratio: According to World Health Organization guidelines, the waist should be measured at the midpoint between the last palpable rib and the top of the iliac crest (upper edge of the pelvis). The hip should be measured at the point of maximum circumference, i.e. the point where the buttocks reach maximum width. Both measures should be taken immediately after the air in the lungs is exhaled. It is important to keep your feet together and your arms in a normal position next to your body. It is advisable to take each measure twice and repeat it if different results are obtained (WHO 2008). The caliper takes the thickness of the abdominal wall at 5 cm in an oblique line towards the navel on the right and left side.

The visceral fat value: will be measured using, in addition to the MRI method, an Inbody electrical impedance equipment, in the first and last session.

TREATMENT

Each patient will have 4 active, automatic plates placed on the abdomen, two on the right side of the midline and two on the left side. Energy will be applied for 50 minutes, controlling the temperature. Subsequently, 15 minutes of Capacitive and Resistive manual electrodes will be applied to the abdomen, simultaneously, 20 minutes of Lymphatic Drainage placing one active plate in the foot and the other in the lumbo-dorsal area. You will be informed that you will only feel comfortable warmth. Five sessions will be applied from Monday to Friday resting Saturday and Sunday, for 2 weeks. Total 10 sessions.

#### DETERMINATION OF BIOCHEMICAL PARAMETERS

For the determination of biochemical parameters of inflammation and adipokines. In coordination with the Echevarne Laboratory Accredited Clinical Laboratory of Barcelona. Blood will be drawn from the patient, the sample is divided into two tubes, one with a yellow cap, which will be left to rest for 30 minutes to obtain serum. The other part will be placed in purple tubes with EDTA. Then, tubes are centrifuged at 4°C for plasma/serum extraction. 4 serum milliliters are placed in 6 tubes of Eppendorf. 300 plasma microliters/tube per are placed in 4 Eppendorf tubes.

All tubes will be frozen until processed at the Biomedical Research Institute of Malaga (IBIMA) Lipid and Arteriosclerosis Research Unit. Medicine at the University of Malaga Andalusia, Spain. IL-6, TNF-alpha, leptin, human adiponectin, human resistin, human ultrasensitive C-reactive protein will be determined. By ELISA and IMMUNOASSAY methods simultaneously.

Samples will be stored by the laboratory at -70°C until the test days. Withdrawn by us and transferred to the University of Malaga for processing using the following tests:

- Human IL-6 QuantiGlo ELISA Kit
- Human TNF-alpha QuantiGlo ELISA Kit
- QuantiGlo Immunoassay Control Set 732 for Human TNF-alpha
- QuantiGlo Immunoassay Control Set 732 for Human IL-6
- Human-Leptin EIA 96 tests
- Human-Adiponectin EIA 96 tests
- Human-Resistin EIA 96 tests
- Ultrasensitive C-Reactive Protein (Human)

#### Statistical analysis and expected results

The statistical analysis of the results will be performed using the Software Package for Social Sciences (SPSS 24.0.).

A Kolmogorov-Smirnov test will be applied, if the data behaves normally, parametric tests will be applied. If not, non-parametric tests will be performed.

The differences between proportions will be analyzed using Fischer's exact test. The differences between the medians will be assessed using the Student's t-test for paired samples and independent samples. To determine the correlation between two quantitative variables, Pearson's correlation coefficient will be used.

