# **BRIEF DESCRIPTION OF THE PROJECT**

The burden of obesity has increased globally in recent decades and its association with insulin resistance and related cardio-metabolic problems. Radio frequency (RF) is a form of high-frequency electromagnetic energy that works by heating tissues. Its action aims to increase cellular metabolism. Its action aims to increase cellular metabolism. Frequencies around 1 MHz are used, which are more effective in the cell, but with high power, adjustable temperature and treatment area greater than 200 cm2, which mechanically destroys the adipose cells, without damaging the skin, blood, vessels, nerves or connective tissues.

The lymphatic system eliminates lidis, reducing tissue volume. Magnetic resonance imaging (MRI) has similar accuracy to CT scans, but with no exposure to ionizing radiation. The MRI method for quantifying abdominal adiposity is effective. Chronic inflammation that lasts a long time is characterized by the presence of lymphocytes, macrophages, proliferation of blood vessels and connective tissue, it is considered a feature of metabolic syndrome, characterized by secretion of inflammatory adipokines usually from adipose tissue, leptin, interleukin (IL-6), tumor necrosis factor  $\alpha$  (TNF- $\alpha$ ), monocyte chemoattractant protein 1 (MCP-1) and resistin. RNA markers involved in apoptotic processes revealed that tissue exposed to RF treatment demonstrated a pro-apoptotic reaction. Therefore, we propose to apply through four channels and four electrodes of 200 cm2 a powerful RF energy raising the temperature and thus reducing visceral fat, evaluating the biochemical parameters of inflammation of the adipocyte.

MAIN OBJECTIVE: To understand the effect of high-power resistive capacitive RF on the decrease of body fat and changes in biochemical markers linked to inflammation.

METHODOLOGY: at the inclusion visit, the patient will be given the information sheet (Annex 1) and, if they agree, they will be asked to sign the informed consent. We aim to declare a difference of 2 points or more as significant, taking the SD from published research that gives around 8.0 with a confidence level of 95%, a power of 80% and a correlation coefficient of 0.70 between the values of abdominal circumference before and after treatment. Noted by Duarte et al. in 2015. We have obtained by EPIDATA that 15 pairs are needed.

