INCLUSION CRITERIA: Men and women aged 20 to 60 years. With Waist to Hip Index Greater than: 0.84 normal for women, 0.94 normal for men. Body Mass Index defined as: Overweight: Between 25-29.9 or Obesity: 30 or higher. Measurement of Visceral Fat (GV) by Inbody greater than 9 which is what is considered Normal. The GV value will be measured using the MRI method in addition to the MRI.

RADIOFREQUENCY PROCEDURE: Each patient will have 4 active, automatic plates placed on the abdomen located two on the right side of the midline and two on the left side. Energy will be applied for 50 minutes, controlling the temperature. Subsequently, 10 minutes of manual capacitive and resistive electrodes will be applied to the abdomen afterwards. 10 minutes of lymphatic drainage by placing one active plate in the foot and the other in the lumbo-dorsal area.

For the determination of biochemical parameters of inflammation and adipokines, the blood will be drawn in coordination with the Echevarne Accredited Clinical Laboratory in Barcelona. Its processing will be carried out at the Biomedical Research Institute of Malaga (IBIMA) Lipids and Arteriosclerosis Research Unit of University of Málaga. IL-6, TNF-alpha, leptin, human adiponectin, human resistin, human ultrasensitive C-reactive protein will be determined by ELISA and IMMUNOASSAY methods simultaneously. A Kolmogorov-Smirnov test will be applied,

if the data behaves normally, parametric tests will be applied. If not, non-parametric tests will be performed.

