## OBJECTIVES

MAIN OBJECTIVE.

- To understand the effect of high-power resistive capacitive radiofrequency on the decrease of body fat and changes in biochemical markers linked to inflammation.
  SIDE OBJECTIVES.
  - 2. To assess the role of radiofrequency in reducing abdominal fat.
  - 3. To assess and compare the decrease in abdominal circumference measured by anthropometric tape measure, Body Mass Index, Waist-to-Hip Ratio and skinfold before and after RF treatment.
  - Evaluate changes in Human IL-6, Human TNF-alpha, Human-Leptin, Human-Adiponectin, Human-Resistin, C-reactive protein values before and after RF sessions. Evaluar y comparar el impacto de la calidad de vida antes y después del tratamiento con radiofrecuencia.
  - 5. To assess and compare the impact of quality of life before and after radiofrequency treatment.

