# **Objective of the study:**

- 🛠 Main
  - Decrease in body fat and biochemical markers.
- Secondary
  - Reduction in abdominal fat.
  - Decrease in abdominal circumference, body mass index.
  - Changes in glycemia, cholesterol and triglycerides.
  - Evaluate and compare the impact of quality of life.

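### No single test is fixed in advance for the six inflammation markers, and no multiplicity rule or exploratory label limits what may be claimed from them

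*Combined protocol and SAP*

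**What the plan says.** The section *Statistical analysis and expected results* states: "A Kolmogorov-Smirnov test will be applied, if the data behaves normally, parametric tests will be applied". It goes on: "If not, non-parametric tests will be performed". The *Brief Description of the Project* repeats the rule: "if the data behaves normally, parametric tests will be applied. If not, non-parametric tests will be performed". The parametric test is then given: "The differences between the medians will be assessed using the Student's t-test for paired samples and independent samples".

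The documents do not say whether the check is applied to the before and after values or to the within-person differences. They do not say whether its critical values are corrected for an estimated mean and SD (Lilliefors), or which non-parametric test is the fallback. No test is assigned to any marker and no transformation is mentioned.

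The main objective under *Objectives* is "To understand the effect of high-power resistive capacitive radiofrequency on the decrease of body fat and changes in biochemical markers linked to inflammation", and the *Brief Description* has nearly the same sentence. The *Objective of the study* list words the main aim as "Decrease in body fat and biochemical markers". The six markers are named only under the side objectives: "Evaluate changes in Human IL-6, Human TNF-alpha, Human-Leptin, Human-Adiponectin, Human-Resistin, C-reactive protein values before and after RF sessions". The *Biochemical Markers* background says they are measured in order to judge whether the treatment is anti-inflammatory. No section gives a multiplicity rule or calls the markers exploratory.

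**The concern.** There are two separate issues.

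First, the test for each marker depends on the data through a rule that can be read in several ways. Two analysts can both comply with the plan and report different p-values for the same marker.

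Second, six markers feed a stated interest in an anti-inflammatory effect, and nothing says how many must change, in which direction, or at what level before that effect may be claimed. One p < 0.05 among six could be presented as a result on the main objective.

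The blanket decrease adds to this. By the documents' own background, adiponectin is anti-inflammatory and falls as adipose tissue grows, so a favourable change would be a rise. Without a direction for each marker, movement either way could be interpreted after the fact.

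**Working it through.** **The plan's own figure.** The sample-size table gives a mean difference of 6.442, an SD of differences of 8.221, 95% confidence and 80% power. A two-sided paired t-test (noncentral t) needs n = 15, with power 80.6%, so the stated 15 pairs reproduce. They concern abdominal circumference. No mean, SD, correlation or target change is given for any marker.

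**Multiplicity (arithmetic).** For six independent tests at 0.05:

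- At least one false positive: 1 − 0.95^6 = 1 − 0.735 = 26.5%. The upper bound under any dependence is 6 × 0.05 = 30%.
- At least one false positive in the favourable direction, if directions were fixed and the tails are symmetric: 1 − 0.975^6 = 1 − 0.859 = 14.1%.
- Bonferroni level: 0.05/6 = 0.0083. Borrowing the circumference effect as an assumption (6.442/8.221 = 0.784), power at that level is 50.9% with 15 pairs and 70.6% with the 20 candidates of *Study Protocol*; 80% needs 24 pairs.

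**Multiplicity (simulated under the planned rule).** Assumptions: lognormal markers, 15 pairs, before/after correlation 0.70 (borrowed from circumference), no effect. The chance of at least one false positive in six, at log-SD 0.5/1.0, is:

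| Test | Independent markers | Between-marker correlation 0.5 |
|---|---|---|
| Gate, uncorrected check | 24.2% / 19.8% | 20.1% / 18.0% |
| Gate, Lilliefors check | 25.8% / 25.2% | 21.4% / 21.9% |
| Fixed paired t on logs | 26.6% / 26.3% | 21.3% / 21.7% |

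Changing the scale therefore does nothing for multiplicity.

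**The gate.** The four readings are an uncorrected or Lilliefors check, applied to differences or to before/after values. The fallback is Wilcoxon signed-rank. Other assumptions are as above, with log-SD 0.5/0.6/0.8/1.0.

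- The four readings do not all choose the same test in 50/61/77/83% of trials with no effect.
- They disagree on p < 0.05 in 1.1/1.4/1.9/2.4% of trials with no effect.
- At an assumed 30% fall they disagree in 3.6/7.2/11.3/11.1% (about 4–12%, allowing for simulation variation).
- Two analysts who differ only in the Lilliefors correction, both on differences, choose different tests in 15–46% of trials. Their verdicts differ in 0.5–1.6% with no effect and 2–8% at a 30% fall.
- Type I error of any single reading is 3.7–4.9%. Always taking the most favourable of the four gives 5.1–5.4%.

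**Scale.** At a 30% fall and 15 pairs, the Lilliefors gate has 4.8/7.5/9.2/7.7 points less power than a paired t-test on logs. At a 15% fall the loss is 3.4/2.9/2.1/1.7 points. If the markers are gamma-shaped with the same CV, the sign reverses: at a 30% fall the log test is 2.4/3.8/4.6/3.6 points lower (for example 0.846 − 0.822 = 0.024).

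**The case against.** The strongest reply is that the harm from the gate is small and that several harsher readings go beyond the documents. Much of this stands.

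- *The gate inflates false positives.* A reader might infer this, but each reading holds its level.
- *The test choice is wide open.* The 50–83% figure is the chance that at least one of four readings differs, not that two analysts differ, and verdicts differ far less often than tests.
- *The plan gives no direction.* It does give one, a decrease for the markers as a class. The fault is that it is not set marker by marker and does not fit adiponectin.
- *The background also contradicts a fall in TNF-alpha.* That background concerns treated tissue and RNA markers, whereas the trial assays blood, so there is no clear conflict.
- *All six markers are primary.* Only the class is in the main objective; the six are named under a side objective. Their status is unclear, which is itself a reason to label them.
- *Paired versus independent is undecided.* The side objective frames the marker question as before versus after, which points to a paired test.
- *A log scale is required.* The documents give no marker distribution, and the analysis scale itself is only inferred from the absence of any stated transformation.
- *A between-group test is the remedy.* *Methodology* mentions two randomised groups, but no section says what a second group receives, and *Treatment* gives every patient active plates.

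The unnamed fallback, the unspecified data and the missing limit on marker claims are untouched by these replies.

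**Conclusion.** The point holds in a limited form and should be corrected. The choice of test depends on an ambiguous check; the cost is modest verdict disagreement, about 1–2% of trials with no effect and 4–12% at a 30% fall. Those figures rest on assumed lognormal markers, log-SD 0.5–1.0, 15 pairs and a borrowed correlation of 0.70.

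The weightier fault is six unadjusted tests serving an anti-inflammatory reading with no multiplicity rule or exploratory label. The 26.5% needs only independence and tests at their nominal 5%; at an assumed between-marker correlation of 0.5 it is about 18–22%. Any power gain from logs cannot be fixed from the documents and can change sign. The reference to medians is probably a slip, since Student's t-test compares means.

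**What to change.** 1. Drop the normality gate for the six markers and name one paired, two-sided before/after test. One option is a paired t-test on log(after/before), reported as a geometric-mean ratio with 95% confidence interval, with Wilcoxon signed-rank as the named sensitivity analysis. A fixed Wilcoxon as the main test would also do. If logs are used, state how values below the assay limit are handled.
2. Change 'medians' to 'means' in the t-test sentence.
3. Label the six markers exploratory and align the main objective in the *Brief Description*, *Objectives* and *Objective of the study*; or name one primary marker. Make no anti-inflammatory claim from a single unadjusted p < 0.05.
4. State the expected direction for each marker, with adiponectin expected to rise.
5. Because candidates also commit to a diet and exercise pattern, do not attribute a before/after marker change to radiofrequency alone. Only if the two groups in *Methodology* are confirmed, and the second is a comparator without radiofrequency, should a treatment claim rest on a between-group comparison adjusted for baseline.

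The cost is wording and more cautious marker conclusions, with no extra patients. If logs prove the wrong scale, a few points of power are lost: 1–5 for gamma-shaped markers and about 2–8 for normal ones at 15 pairs (for example 0.641 against 0.621, and 0.873 against 0.792).

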#### METHODOLOGY

At the inclusion visit, the patient will be given the information sheet (Annex 1) and, if they agree, they will be asked to sign the informed consent. Once included in the study, they will be randomly assigned to one of the two study groups in order of consecutive inclusion.

The project will be presented to the Ethics Committee of the Autonomous University of Barcelona UAB.

SAMPLE SIZE CALCULATION

The aim of this study was to assess the difference between a decrease in the diameter of the abdominal circumference in a group of women, before and after radiofrequency treatment. The aim is to be able to declare a difference of 2 points or more as significant, taking the SD from published research that gives around 8.0 with a confidence level of 95%, a power of 80% and a correlation coefficient of 0.70 between the values of abdominal circumference before and after treatment. These are taken from the article published by Duarte et al. in 2015 (Duarte et al, 2015), and the following results are obtained according to EPIDATA: 15 pairs of data will then be taken: Before and after the application of RF.

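### The two-group comparison has only an unadjusted independent-samples t-test on an unspecified variable; adjusting for the baseline already collected would be more precise, by an amount that depends on what is tested and on the before-after correlation

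*Combined protocol and SAP*

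**What the plan says.** Under METHODOLOGY, once participants are included, "they will be randomly assigned to one of the two study groups in order of consecutive inclusion". The allocation ratio and the second group's treatment are not given.

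The sample-size text in the same section plans a before value and an after value for each person: "15 pairs of data will then be taken: Before and after the application of RF". It assumes "a correlation coefficient of 0.70 between the values of abdominal circumference before and after treatment" and describes "taking the SD from published research that gives around 8.0". It names a difference of 2 points as the target. The software printout that follows uses a difference of 6.442 and an SD of differences of 8.221, and returns 15 pairs. The section headed STUDY PROTOCOL plans 20 participants.

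The section Statistical analysis and expected results is short. After a Kolmogorov-Smirnov check it lists Fisher's exact test for proportions, the Student "t-test for paired samples and independent samples", and Pearson's correlation. For data that fail the normality check it says "If not, non-parametric tests will be performed", without naming them. No regression, analysis of covariance or other baseline adjustment appears in the documents. The text does not tie the independent-samples test to the randomised contrast, and it does not say which variable that test would be applied to.

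**The concern.** If there are two randomised groups, the contrast between them is what separates the effect of radiofrequency from everything else that changes over the same weeks. That includes the diet and exercise pattern to which participants commit (candidate criteria after STUDY PROTOCOL), drift, and regression to the mean. The independent-samples t-test is the only named parametric method that can make this contrast on a continuous outcome.

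Two things follow.

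- The baseline is collected but not used as a covariate. With 15 to 20 people, chance baseline imbalance can be large, and the baseline carries much of the information about the after value.
- The tested variable is left open, so the choice between after values and changes could be made once the data are seen. Which of the two is more precise depends on a correlation that the plan does not settle.

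Paired and independent tests are also listed together without saying which one supports the conclusion. That leaves room for comparing within-group p-values across groups, which is not a test of a group difference.

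**Working it through.** **Inputs.** SD 8.0 and r = 0.70 (sample-size text); difference 6.442 and SD of differences 8.221 (printout); difference 2 (text); 20 participants (STUDY PROTOCOL) or 15 (printout). Assumptions made here: two-sided 5%, near-equal allocation, equal SD before and after and in both groups. The 6.442 is a before-after difference in the plan. It is borrowed below as an assumed between-group difference, because the plan gives none.

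**Step 1: the plan's own figure.** A paired t-test with difference 6.442 and SD of differences 8.221 (noncentral t) needs 15 pairs, with power 80.6%. The printout is reproduced. The text's inputs do not lead there: with difference 2, SD 8.0 and r = 0.70, the SD of differences is 8.0 × √(2 × 0.30) = 6.197, and 78 pairs are needed.

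**Step 2: which correlation.** If 8.0 is the SD at each time, the SD of differences satisfies 8.221² = 2 × 8.0² × (1 − r). So r = 1 − 67.58/128 = 0.472. The plan therefore supports two values, 0.70 and about 0.47, and both are carried forward.

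**Step 3: relative variance of the group difference.** After values: 1. Changes: 2(1 − r). Baseline-adjusted: 1 − r². Estimating the slope multiplies the adjusted variance by about 1 + 1/(N − 4), which is 1.0625 at N = 20.

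| | r = 0.70 | r ≈ 0.47 |
|---|---|---|
| Changes, 2(1 − r) | 0.60 | 1.056 |
| Adjusted, 1 − r² | 0.51 | 0.777 |
| Loss if after values are tested | 1 − 0.51 = 49% | 1 − 0.777 = 22% |
| Loss if changes are tested | 1 − 0.51/0.60 = 15% | 1 − 0.777/1.056 = 26% |
| After values, N = 20 | 1 − 0.51 × 1.0625 = 46% | 17% |
| Changes, N = 20 | 1 − 0.51 × 1.0625/0.60 = 10% | 22% |

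Loss means loss of precision (1/variance) relative to the adjusted model. On the standard-error scale the effect is smaller: at r = 0.70, without the slope cost, the SE is 40% larger on after values (1/√0.51 = 1.40) and 8.5% larger on changes (√(0.60/0.51) = 1.085).

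**Step 4: standard error and power.** SE = 8.0 × √factor × √(1/n₁ + 1/n₂), with the slope cost included for the adjusted model. At 10 v 10 and r = 0.70:

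- after values: 8.0 × √0.2 = 3.58
- changes: 3.58 × √0.60 = 2.77
- adjusted: 3.58 × √(0.51 × 1.0625) = 2.63

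Power from the noncentral t (N − 2 degrees of freedom, N − 3 for the adjusted model):

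| Setting | After | Change | Adjusted |
|---|---|---|---|
| Difference 6.442, 10 v 10, r = 0.70 | 40% | 59% | 64% |
| Difference 6.442, 10 v 10, r ≈ 0.47 | 40% | 38% | 46% |
| Difference 6.442, 8 v 7, r = 0.70 | 30% | 46% | 48% |
| Difference 6.442, 8 v 7, r ≈ 0.47 | 30% | 29% | 34% |
| Difference 2, 10 v 10, r = 0.70 | 8% | 11% | 11% |

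The order of the two t-tests reverses between the two correlations. The adjusted model has the highest power for 6.442 in every setting shown. For a difference of 2 the choice of analysis hardly matters.

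**The case against.** The strongest reply is that the plan is a before-after study in all but one sentence. The objectives that name a comparison compare before with after, the calculation is for paired means, every patient is described as receiving active plates, and STUDY PROTOCOL describes one treatment for all 20 candidates. If only one group is run, there is no group contrast and this point does not arise. That stands as a condition on the point. It does not remove it, because METHODOLOGY says in plain terms that people are "randomly assigned to one of the two study groups", and the analysis section lists a test for independent samples.

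A reader might also infer more than the documents support, in three ways.

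- **That about half the precision is lost.** This requires the t-test to be run on after values at r = 0.70. The plan does not say so, and its before-after framing makes changes at least as likely. On changes at r = 0.70 the loss is 15%, or about 10% with 20 participants.
- **That the loss applies to the main outcomes.** The 0.70 is given for abdominal circumference only. The main objective concerns body fat and inflammatory markers, for which no correlation is given.
- **That the t-test is wrong.** Under randomisation, a t-test on after values or on changes is a valid comparison. The issue is efficiency and an unspecified choice, not bias. Nor does the plan say that within-group p-values will be compared; it only fails to exclude it.

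It is also fair to say that the undefined second group, and a sample size that addresses only the before-after change, are larger problems than the efficiency of the group comparison.

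**Conclusion.** The point holds as a conditional improvement. If the two-group design is run, the plan compares groups on continuous outcomes with an unadjusted t-test on an unstated variable, although each participant's baseline is available. For abdominal circumference, the precision lost against a baseline-adjusted model is between about 10% and 49%, depending on whether after values or changes are tested, whether r is 0.70 or about 0.47, and whether the cost of estimating the slope is counted. The figures rest on equal SDs of 8.0 and near-equal groups; those at r of about 0.47 further rest on 8.0 being the SD at each time.

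The case for adjustment does not depend on which correlation is right, since the adjusted model is more precise than both t-tests at each. A reader might infer that adjustment rescues the comparison. It does not: even for a group difference as large as 6.442, power with 20 participants is at most 64%, and for the text's difference of 2 it is about 8 to 11% whatever the analysis. For MRI fat, the markers and quality of life, the size of the gain cannot be stated from the documents.

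**What to change.** First define the second group, or state that there is only one. If there are two, amend Statistical analysis and expected results as follows:

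- For the randomised comparison of continuous outcomes, replace the independent-samples t-test by a linear model of the after value on group and the same participant's before value, with the markers on the log scale. Report the adjusted group difference with its 95% CI.
- If a non-parametric fallback is kept, name it and apply it to the same baseline-adjusted contrast, for example rank-based analysis of covariance.
- State that within-group before-after tests are descriptive and are not compared across groups.

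The cost is a few sentences and one degree of freedom. No new data are needed, and SPSS, which the plan already names, can fit the linear model.
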